#### 5.3.2.4. Duration of response (DoR)

A responder is defined as a subject who achieved objective response (see [Section 5.3.2.3](#)). Among the responders, DoR in months will be calculated from the date of the first occurrence of response to the date of first documented disease progression or death, whichever comes earlier. See [Table \(5.3.1\) 1](#) for the censoring rules.

Duration of response = (Earliest Date of Death/Progression – Date of First Confirmed PR/CR + 1)/30.4375.

DoR may be analysed by IRC as primary analysis and by Investigator as sensitivity analysis. If there are at least 5 responders, Kaplan-Meier plot of DoR may be generated.

Listing on DoR will be provided for responders.

#### 5.3.2.5. Time to response (TTR)

Time to response is defined as the time (in months) from the C1D1 to the date of first occurrence of confirmed response per RECIST v1.1. TTR may be analysed by IRC as primary analysis and by Investigator as sensitivity analysis.

Time to response = (Date of First Confirmed PR/CR – Day 1 Date + 1)/30.4375.

Listing on TTR will be provided for responders.

## 5.4. Safety analysis

Unless specified otherwise, all safety analyses will be performed on the SAS as defined in [Section 3.1](#). The analysis of the safety data will be descriptive, and no testing is planned.

### 5.4.1. Adverse events

Treatment-emergent adverse event (TEAE) is defined as adverse events that take place between the first study drug intake date (inclusive) and last study drug intake date +28 days (inclusive). TEAE will be summarized according to Medical Dictionary for Regulatory Activities (MedDRA) by SOC and/or PT, severity (based on NCI CTCAE v 5.0 grading as assessed by the Investigator), seriousness, and relation to study drug.

If the assessment of the relationship to study drug is missing for an AE, this AE will be assumed as related to study drug. Missing grade will be left as missing.

Multiple occurrences of the same event in the same subject will be counted only once in the tables within treatment-emergent period using the worst (maximum value) grade. Summaries will be provided for all grades combined and for grade  $\geq 3$ . Missing grades, if any, will be included in the “all grades” category.

The AE tables will be sorted as indicated in [Table \(5.4.1\) 2](#).

**Table (5.4.1) 2 – Sorting of AE tables**

AE presentation	Sorting rules
SOC and PT	By the alphabetical SOC order and decreasing frequency of PTs
SOC	By the alphabetical SOC order
PT	By decreasing frequency of PTs

### Analysis of all adverse events

The overview of TEAE in the below categories will be generated:

- TEAE.
- TEAE leading to dose modification (interruption / reduction).
- TEAE related to study drug.
- TEAE leading to study drug withdrawal.
- TEAE related to study drug leading to dose modification.
- TEAE related to study drug leading to study drug withdrawal.
- Grade  $\geq 3$  TEAE.
- Grade  $\geq 3$  TEAE related to study drug.
- Common TEAE ( $\geq 10\%$  in all subjects).
- Grade  $\geq 3$  Common TEAE ( $\geq 10\%$  in all subjects).
- Grade  $\geq 3$  Common TEAE ( $\geq 10\%$  in all subjects) related to study drug.
- Treatment-emergent serious AE.
- Treatment-emergent serious AE related to study drug.
- Treatment-emergent fatal AE.
- Treatment-emergent fatal AE related to study drug.

- The AE summaries of [Table \(5.4.1\) 3](#) will be generated with number (%) of subjects experiencing at least one event.

**Table (5.4.1) 3 – MedDRA levels of adverse events**

Type of AE	MedDRA levels
TEAE	SOC and PT
	SOC
	PT
TEAE leading to dose modification (interruption / reduction)	SOC and PT
TEAE related to study drug	SOC and PT
TEAE leading to study drug discontinuation	SOC and PT
TEAE related to study drug leading to study drug discontinuation	SOC and PT
Grade $\geq 3$ TEAE	SOC and PT
Grade $\geq 3$ TEAE related to study drug	SOC and PT
Common TEAE ( $\geq 10\%$ in all subjects)	PT
Treatment-emergent SAE	SOC and PT
Treatment-emergent SAE related to study drug	SOC and PT
Treatment-emergent fatal AE	SOC and PT

The overview of treatment duration adjusted incidence rate of TEAE for subjects with an event per person-year will also be generated.

All AEs will be listed by subjects and TEAE will be flagged in the listings.

#### **Analysis of adverse events of special interest (AESIs)**

QT prolongation event using the search criterion of SMQ (Broad) of Torsade de pointes/QT prolongation will be selected.

The AESI will be summarized for the following:

- Any grades by PT.
- Grade  $\geq 3$  by PT.
- Any grades related to study drug by PT.

Time to onset of the AESI event will be summarized quantitatively and categorically by  $\leq 15$  days, 16-30, 31-45, 46-60, and  $>60$  days for all grade and Grade 2 or higher AEs.

#### **Analysis of deaths**

On-treatment deaths (within the 28 days after last dose of study drug) and all deaths with the reasons of deaths will be summarized. Listing of individual subjects will be provided.

In addition, all-cause mortality will be summarized including the deaths  $\leq 30$  days of the first and last dose, and  $\leq 60$  days of the first and last dose.

#### 5.4.2. Clinical laboratory evaluation

The hematology and chemistry parameters will be presented in both actual values and changes from baseline as appropriate by scheduled visits. Coagulation, urinalysis and pregnancy test results will be presented in listings. They will be converted into standard international units.

- Hematology
  - Hemoglobin, red blood cell (RBC) count, white blood cell (WBC) count, neutrophils count, lymphocytes count and differential (% neutrophils, % bands), platelet count.
- Serum chemistry
  - Sodium, potassium, total calcium, magnesium, phosphate, albumin, glucose, blood urea nitrogen (BUN), creatinine, uric acid, lactate dehydrogenase (LDH), alkaline phosphatase (ALP), aspartate aminotransferase (AST), alanine aminotransferase (ALT), total bilirubin, direct bilirubin.
- Coagulation Studies
  - Prothrombin time (PT) and/or international normalized ratio (INR), activated partial thromboplastin time (aPTT).
- Urinalysis
  - Color and appearance; pH, specific gravity, ketones, protein, glucose, bilirubin, nitrite, urobilinogen, and occult blood; and microscopic inspection of sediment.
- Pregnancy Test
  - For female subject, a serum pregnancy test will be performed at Screening; a serum or urine pregnancy test must be conducted and confirmed negative on the first day of study drug administration before dosing and on Day 1 of every cycle.

Shift tables from baseline to worst value based on CTCAE V5.0 grade will be presented, including:

- White blood cell (low).
- Absolute neutrophil count (low).
- Hemoglobin (low).
- Platelet count (low).
- Total Bilirubin (high).
- Alkaline Phosphatase (high).
- ALT (high).
- AST (high).
- Sodium (low).
- Potassium (low/high).
- Phosphate (low).

In addition, subjects with liver dysfunction will be presented in a listing. Liver dysfunction is defined as elevated ALT or AST of  $\geq 3x$  ULN and associated with increase in total bilirubin  $\geq 2x$  ULN ( $\pm 10$  days).

#### 5.4.3. Vital signs, clinical examination and other observations related to safety

##### 5.4.3.1. Vital signs and clinical examination

Vital signs (except height) will be presented as both actual values and changes from baseline by scheduled visits. Vital sign measurements will also be listed.

#### 5.4.3.2. Electrocardiogram

Descriptive statistics for the actual values and changes from baseline over time will be summarized for each ECG parameter: QT (msec), RR interval (msec) and QTcF (Fridericia's correction). QTcF is calculated as QTcF = QT/cube root of RR interval.

The proportion of subjects with maximum post-baseline absolute QTcF intervals that fall into following categories will be presented:

- $\leq 450$  msec.
- $>450$  and  $\leq 480$  msec.
- $>480$  to  $\leq 500$  msec.
- $>500$  msec.

The proportion of subjects who have a maximum post-baseline change from baseline in QTcF intervals of the following categories will be presented:

- $\leq 0$  msec.
- $>0$  to  $\leq 30$  msec.
- $>30$  to  $\leq 60$  msec.
- $>60$  msec.

A listing of subject-level ECG measurement will be provided.

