8.6. Definition of adverse event of special interest

An adverse event of special interest (AEOSI) is one of scientific and medical interest or concern regarding the IMP for which recording rules, special documentation such as hospital records and/or adjudication committee could be appropriate. It may be a serious or non-serious AE that may require further investigation in order to be characterized and understood.

AEOSI include:

Any QT prolongation event assessed as Grade 2 or worse (e.g., QTcF interval longer than 480 msec or any QTcF interval variation that is equal or more than 60 msec than the reading at baseline) with Torsade de pointes or polymorphic ventricular tachycardia or signs/symptoms of serious arrhythmia, irrespective of the seriousness of the event, should be reported as an AEOSI to the Sponsor within 24 hours. See [Section 8.11.1](#) for further details on managing subjects with QTcF Prolongation. See [Appendix 8](#) for Fridericia's formula.

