10.1.2.5.3. Other Safety Data

Descriptive statistics for the actual values and/or the changes from baseline of vital signs (including systolic and diastolic blood pressure, heart rate, respiratory rate, and temperature) over time will be summarized.

Descriptive statistics of ECOG PS over time will be summarized by frequency. Shift tables may be provided for ECOG PS from baseline to worst value of post-baseline assessments.

Categorical analysis of QTcF intervals may be performed. Maximum QTcF intervals and maximum changes from baseline may also be summarized similarly in a separate display. ECG abnormalities if collected will be presented in a data listing.

Additional safety analyses may be performed if deemed necessary.

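### SAP 5.4.3.2 gives RR in msec and divides QT by its cube root without converting to seconds, so QTcF programmed as written is ten times too small

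*SAP*

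**What the plan says.** SAP Section 5.4.3.2 lists the ECG parameters to be summarised as "QT (msec), RR interval (msec) and QTcF", with Fridericia's correction named in parentheses after QTcF. The next sentence gives the derivation: "QTcF is calculated as QTcF = QT/cube root of RR interval". Msec is the only unit the SAP attaches to RR.

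The section then uses the derived value in two categorical tables:

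- Maximum post-baseline QTcF: ≤450, >450 to ≤480, >480 to ≤500 and >500 msec. The SAP commits to this table: "The proportion of subjects with maximum post-baseline absolute QTcF intervals that fall into following categories will be presented".
- Maximum change from baseline: ≤0, >0 to ≤30, >30 to ≤60 and >60 msec. It commits to this one too: "The proportion of subjects who have a maximum post-baseline change from baseline in QTcF intervals of the following categories will be presented".

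By-visit descriptive statistics and a subject-level ECG listing are also planned.

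Protocol Appendix 8 gives the same formula with no units. Elsewhere the protocol reads QTcF on the ordinary scale of hundreds of msec, for example "QTcF interval longer than 480 msec" in Section 8.6.

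**The concern.** The category limits match a QTcF in the hundreds of msec, which the Fridericia formula gives only when RR is in seconds. With RR in msec, the only unit stated, the formula gives values in the tens. The derivation and the tables built on it are therefore on different scales.

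The error also runs in the reassuring direction: a literal program would show no QTcF prolongation at all. Protocol Section 2.4 names QT prolongation as an important identified risk in all indications, and Section 8.6 makes it the adverse event of special interest. SAP Section 5.4.3.2 holds the SAP's only planned summaries of measured QTcF.

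**Working it through.** The documents contain no worked QTcF value, so there is no stated figure to reproduce. The check is direct arithmetic. The formula, units and category limits come from SAP Section 5.4.3.2. The individual QT and RR values below are illustrative assumptions, because the documents give no ECG data.

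**The factor**

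- As written: QTcF_w = QT(msec) / RR(msec)^(1/3)
- With RR in seconds: QTcF_s = QT(msec) / [RR(msec)/1000]^(1/3)
- Ratio: QTcF_s / QTcF_w = 1000^(1/3) = 10, for every QT and RR

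Example: QT 400 and RR 1000 give 400/10 = 40 as written, and 400/1 = 400 with RR in seconds.

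Over an assumed grid of QT 360 to 600 msec and RR 500 to 1500 msec (heart rate 120 to 40 per minute), the as-written values run from 31.4 to 75.6. With RR in seconds they run from 314.5 to 756.0.

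**Absolute categories.** The QT needed to exceed a QTcF of 450 is 450 × RR^(1/3), with RR in the unit used:

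| RR (msec) | Heart rate (per min) | QT needed, as written | QT needed, RR in seconds |
|---|---|---|---|
| 600 | 100 | 450 × 8.434 = 3795 | 380 |
| 800 | 75 | 450 × 9.283 = 4177 | 418 |
| 1000 | 60 | 450 × 10 = 4500 | 450 |
| 1200 | 50 | 450 × 10.627 = 4782 | 478 |

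If QT cannot exceed RR, an as-written value above 450 requires RR above 450^1.5 ≈ 9546 msec. So no subject could leave the ≤450 category.

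**Change categories.** Changes shrink by the same factor. An as-written change above 30 needs a true change above 30 × 10 = 300 msec, and one above 60 needs 60 × 10 = 600 msec.

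Worked case, with baseline QT 380 at RR 900 and post-baseline QT 460 at RR 850:

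- RR in seconds: 380/0.9^(1/3) = 393.6 and 460/0.85^(1/3) = 485.6, a rise of 92.0 msec. Categories: >480 to ≤500, and >60.
- As written: 380/900^(1/3) = 39.36 and 460/850^(1/3) = 48.56, a rise of 9.20. Categories: ≤450, and >0 to ≤30.

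**Search for a conversion elsewhere.** Protocol Appendix 8 has no units. SAP Appendix A (data handling conventions) has no ECG unit rule. The sentence on standard international units in SAP Section 5.4.2 concerns laboratory results. SAP Section 7 records no change to planned analyses.

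**The case against.** The strongest reply is that the SAP names a standard method. The formula sentence can be read as shorthand for it, with msec in the parameter list serving as the reporting unit for RR rather than the input unit. The category limits leave only one workable scale. With about 10 subjects planned, means and listed values near 40 would be obvious at the first review of output. The tables, listings and graphs templates are a separate document and may state the conversion; that cannot be checked here. Finally, safety analysis is descriptive, and the protocol makes the categorical table optional: "Categorical analysis of QTcF intervals may be performed".

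Most of this stands as a limit on the consequence. A competent programmer would probably convert RR, and a literal program would probably be caught. It does not make the rule right. The SAP says how QTcF is calculated, gives msec as the only unit for RR, and is correct only if the programmer departs from it. Its category limits show that the rule conflicts with its own section; they do not repair it. The protocol may leave the categorical analysis optional, but the SAP commits to presenting it.

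The limits on scope also stand. The AESI tables choose events by MedDRA query: "QT prolongation event using the search criterion of SMQ (Broad) of Torsade de pointes/QT prolongation will be selected". Investigator AE grading, AESI reporting, QT management at the sites and the primary endpoint do not use this derivation either.

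**Conclusion.** The concern holds. The SAP derivation is wrong in its stated unit, and QTcF computed from it is too small by a factor of exactly 10. That factor needs no assumption about ECG values. The conclusion that every subject would be at or below 450 msec rests on physiologically possible QT and RR values, but the margin is so wide that the range chosen does not matter.

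The consequence is conditional on literal programming and is limited to the descriptive and categorical QTcF outputs of SAP Section 5.4.3.2. It should be corrected because it concerns an important identified risk and errs towards false reassurance. It does not threaten the trial's primary conclusion. Protocol Appendix 8 omits a unit but is not itself wrong.

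**What to change.** In SAP Section 5.4.3.2, replace the formula with:

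QTcF (msec) = QT (msec) / [RR (msec)/1000]^(1/3)

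This is a one-line SAP change. It needs no new data and no protocol amendment, and it alters no clinical rule. Stating that RR is in seconds in Protocol Appendix 8 is an optional clarification that can wait for an amendment made for other reasons.

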#### 5.4.3.3. Left Ventricular Ejection Fraction (LVEF)

The LVEF data will be listed.

#### 5.4.3.4. ECOG Performance Status (PS)

The ECOG PS will be summarized by visit, and by shift tables from baseline to worst values across all visits.

A by-subject listing will be provided.

### 5.5. Quality of Life

In general, descriptive statistics will be used to summarize the individual items and sub-scale scores of HRQOL (EORTC-QLQ-C30, and EORTC-QLQ-BIL21) and EQ-5D-5L data at each scheduled assessment time point. Data listings will also be provided by each endpoint and visit for each subject.

#### 5.5.1. EORTC-QLQ-C30

The QLQ-C30 is a cancer specific instrument that contains 30 questions and provides a multi-dimensional assessment of health related QoL. The QLQ-C30 incorporates five functional scales (Physical functioning, Role functioning, Cognitive functioning, Emotional functioning and Social functioning), three symptom scales (Fatigue, Pain and Nausea/Vomiting), six additional single items (Dyspnoea, Insomnia, Appetite Loss, Constipation, Diarrhoea and Financial Difficulties) and a global health status (GHS) as symptoms commonly reported by cancer patients and the perceived financial impact of the disease.

The raw scores are linearly transformed to scale scores in the range of 0-100 based on EORTC guidelines. Higher scores in the global and functioning scales and lower scores in the symptom/single scales indicate better quality of life. See [Appendix C](#) for the calculation of raw score and transformed scale score.

Transformed scores for each scale and the absolute change from baseline will be summarized by visit.

### 5.5.2. EORTC-QLQ-BIL21

The QLQ-BIL21 is for assessing the QoL in subjects with cholangiocarcinoma, it consists of five scales and three single items,

- 5 scales (18 items): eating symptoms (4 items), jaundice symptoms (3 items), tiredness (3 items), pain symptoms (4 items), anxiety symptoms (4 items).
- 3 single-item assessments related to treatment side-effects, difficulties with drainage bag/tubes, concerns regarding weight loss.

Similar to QLQ-C30, QLQ-BIL21 scores will be transformed to scale scores as well and will be summarized by visit.

### 5.5.3. EQ-5D-5L

The EQ-5D-5L incorporates the EQ-5D descriptive system and a visual analogue scale (VAS).

The EQ-5D-5L descriptive system comprises the following 5 dimensions: mobility, self-care, usual activities, pain/discomfort and anxiety/depression. Each dimension has 5 levels: no problems, slight problems, moderate problems, severe problems and extreme problems. For each dimension, the number and percentage of subjects in each category will be summarized by visit.

The EQ VAS records the respondent's self-rated health ranging between 0 (worst health) and 100 (best health). Summary statistics for VAS score and the absolute change from baseline will be reported by visit.

### 5.6. PK and PK/PD analyses

PK-related analyses on Pharmacokinetic Analysis Set (PAS) and Pharmacodynamic Analysis Set will be documented and reported separately.

### 5.7. Exploratory analysis

Not applicable.

### 5.8. Biomarkers analysis

Analyses for PD biomarkers will be documented and reported separately.

CL2-95031-008 - Statistical Analysis Plan | VV-TMF-169574 | 1.0

*Ivosidenib*

*CL2-95031-008 - Statistical Analysis Plan - Final version 1.0*

## **6. INTERIM ANALYSIS**

Not applicable.

**7. CHANGES TO PROTOCOL-PLANNED ANALYSES**

Not applicable.

## 8. APPENDICES

### 8.1. Appendix A: Data handling conventions

#### 8.1.1. General conventions

Summary statistics will be presented by treatment and scheduled visit, unless stated otherwise. Unless otherwise specified, descriptive statistics for continuous data will include the number of subjects with data to be summarized (n), mean, standard deviation, median, Q1, Q3, minimum, and maximum.

Descriptive statistics for categorical/qualitative data will include frequency counts and percentages. The total number of subjects will be used as the denominator for percent calculations, unless stated otherwise.

Descriptive statistics associated with time-to-event analyses will include the number of events, the number of subjects censored, 25% quartile, median, 75% quartile, and 95% CI for median. These statistics will be presented for all time-to-event analyses, unless stated otherwise.

Listings will be provided for selected endpoints. Listings will be sorted by site, treatment, and subject IDs.

#### 8.1.2. Relative study days

All data listings that contain an evaluation date will contain a relative study day.

Study days are numbered relative to C1D1 starting from Day 1 for all outputs. The preceding day is Day -1, the day before that is Day -2, etc. There is no Day 0.

#### 8.1.3. Baseline values

Unless otherwise specified, the baseline value is defined as the latest value prior to the start of study drug administration. In case subjects are not exposed, the latest assessment will be considered as baseline. Values collected at unscheduled visits prior to the start of the study drug administration will be included in the calculation of baseline values. In majority of cases, C1D1 assessment should be treated as the baseline as the study protocol requires assessment to be done pre-dose at C1D1.

#### 8.1.4. Unscheduled Visits and Visit Windows

Unscheduled visits will not be mapped and will not be included in the summary statistics per visit tables. However, they will be included in the data listing as well as the shift tables.

## **8.2. Appendix B: Handling of missing data**

### **8.2.1. Missing data handling for efficacy data**

Refer to [Table \(5.3.1\) 1](#) for missing response assessment and censoring rules.

#### **8.2.1.1. Missing/Partial Dates in On-study Anticancer Therapies**

On-study anticancer therapy with start dates that are completely or partially missing will be imputed as follows:

1. If the start date has month and year but day is missing, the 15 of the month will be used.
2. If the start date has year, but day and month are missing, July 1 will be used.

On-study anticancer therapy with stop dates that are completely or partially missing will be imputed as follows:

1. If the stop date has month and year but day is missing, the last day of the month will be assigned.
2. If the stop date has year, but day and month are missing, December 31 will be assigned.
3. If the stop date misses day, month and year, the event will be considered as ongoing.

If the imputed date is before the last dosing date, the last dosing date will be used as the on-study anticancer therapy start date. If the imputed date is after the death date, then the death date will be used. If the imputed stop date is before start date, the stop date will be used as the start date.

This imputation rule will only be used in efficacy endpoints derivation (such as PFS, OS). The listing of post-study anticancer therapy will not apply imputation rules.

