**Table (5.3.1) 1 Handling of Missing Response Assessment and Censoring for the Primary Analysis of PFS**

Situation	Date of Censoring
No baseline assessment and no death.	Date of the Cycle 1 Day 1
Alternate anticancer systemic treatment started before documented progression (PD) per RECIST 1.1 or death.	Date of last adequate assessment prior to the start of alternate anticancer treatment 
No adequate post-baseline assessment and no death.	Date of the Cycle 1 Day 1
No documented PD per RECIST 1.1 or death before data cut-off date or before permanently discontinued from the study.	Date of last adequate assessment 

Situation	Date of Censoring
Documented PD per RECIST 1.1 or death following a long gap from the previous adequate assessment (e.g., 2 or more consecutive missed scheduled disease status assessments). The long gap is defined as $\geq 95$ days (ie, 12 weeks + 10 days per the protocol defined visit window). If no adequate assessment prior to minimum of (PD, death), the long gap is calculated from the Cycle 1 Day 1.	Date of last adequate assessment prior to the first occurrence of 2 or more consecutive missing scheduled assessments

 Adequate disease assessment is defined as a response assessment other than “not evaluable.” If there is no adequate response assessment prior to the start of anticancer treatment, it will be censored at the date of Cycle 1 Day 1.

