**8.2.2.2. Missing/Partial Dates at Screening Visits**

The following rules apply to dates recorded during the screening visits (e.g., prior anticancer therapy).

*Missing day only*

- The first day of the month will be used.

*Missing day and month*

- If the year is the same as the year of the earliest inform consent date at screening, the 1st of January will be used.
- If the year is before the year of the earliest inform consent date at screening, the 15th of June will be used.

*Missing day, month and year*

- No imputation can be done.

If the imputed end date is before the start date, the start date will be used as the end date. If the imputed dates are after the inform consent date at screening, then the inform consent date will be chosen.

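### A partly missing start date for later anticancer therapy is imputed without checking it against documented progression, so an IRC progression that came first can be censored in the primary PFS analysis

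*SAP*

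**What the plan says.** SAP 8.2.1.1 gives two imputations for a partial start date: "If the start date has month and year but day is missing, the 15 of the month will be used" and "If the start date has year, but day and month are missing, July 1 will be used". Two checks follow. The floor is "If the imputed date is before the last dosing date, the last dosing date will be used as the on-study anticancer therapy start date". The cap is "If the imputed date is after the death date, then the death date will be used". The subsection says that the imputed dates serve the derivation of efficacy endpoints and names PFS.

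In SAP Table (5.3.1) 1, new systemic therapy begun before documented progression or death leads to censoring at the "Date of last adequate assessment prior to the start of alternate anticancer treatment". The table makes no exception for an imputed start. SAP 5.3.2.2 and 5.3.2.4 apply the same rules to Investigator PFS and to duration of response.

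Subjects can be off drug before progression. Under Protocol 4.1.1, scans continue regardless of dose delays, and subjects who stop for reasons other than progression stay on the scan schedule. Protocol 8.10.1.1 allows dose delays of up to 28 days. Protocol 6.1.1 dates end of treatment from the first withheld dose when drug is not restarted.

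**The concern.** New therapy commonly follows progression, so a guessed start that lands before an observed progression is often the wrong order of events. The plan nevertheless lets the guess decide. The progression is removed as an event and the subject is censored at an earlier scan. In a trial of about 10 subjects, one event is a tenth of the data, and the quantity affected is the primary estimate, the Kaplan-Meier 6-month rate by IRC. The rule is fully stated and gives a wrong result in this situation, so it cannot be treated as a detail left to programming.

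**Working it through.** **1. The plan's own figure.** Inputs from SAP 1.3: 10 enrolled, 10% dropout, null 2.6%, target 32%, one-sided 0.05. Evaluable: 10 × 0.9 = 9. Rejecting at 2 or more of 9 gives an exact level of 1 − 0.974⁹ − 9 × 0.026 × 0.974⁸ = 0.0216 and power of 0.837, which matches the stated 84%. With 10 evaluable the values are 0.0265 and 0.879.

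**2. When an event is lost.** Let I be the later of the imputed date and the last dose. A progression that preceded the true start is lost when I is earlier than the progression date. Assumed dates:

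| Recorded | Last dose | Progression | True start | I | Result |
|---|---|---|---|---|---|
| May, day missing | 20 Apr | 20 May | 27 May | 15 May | censored |
| May, day missing | 19 May | 20 May | 27 May | 19 May | censored |
| May, day missing | 22 May | 20 May | 27 May | 22 May | event kept |
| Year only | 1 Jun | 5 Aug | 20 Aug | 1 Jul | censored |
| Year only | 6 Aug | 5 Aug | 20 Aug | 6 Aug | event kept |

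**3. How wide the window is.** With the day missing, progression must fall on the 16th or later and the true start by the 31st, so the gap is at most 31 − 16 = 15 days. Taking the true start as uniform over a calendar year and the last dose before progression, the share of start days on which the event is lost is:

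| Gap, progression to start (days) | 1 | 3 | 7 | 10 | 14 | 15 | 16 or more |
|---|---|---|---|---|---|---|---|
| Event lost | 48% | 41% | 28% | 18% | 5% | 2% | 0% |

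If the last dose is on or after the progression date, the share is 0% at every gap. The year-only rule has a wider window.

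**4. Effect on the 6-month rate.** These are invented data on the 6-weekly scan schedule, with one progression moved to censoring at the previous scan.

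First illustration: 3 progressions at week 6, 2 at week 12, 2 at week 18, 1 at week 24, and 2 subjects event-free.
- No event lost: (7/10)(5/7)(3/5)(2/3) = 0.200
- Week 6 event lost, censored at C1D1: (7/9)(5/7)(3/5)(2/3) = 0.222
- Week 12 event lost: (7/10)(5/6)(3/5)(2/3) = 0.233
- Week 18 event lost: (7/10)(5/7)(3/4)(2/3) = 0.250
- Week 24 event lost: (7/10)(5/7)(3/5) = 0.300

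Second illustration: 3 progressions at 1.4 months, 1 at 2.8, 1 at 4.1, 2 at 5.5, and 3 subjects event-free.
- No event lost: (7/10)(6/7)(5/6)(3/5) = 0.300
- One 5.5-month event lost: (7/10)(6/7)(5/6)(3/4) = 0.375, the largest shift
- One 1.4-month event lost: (7/9)(6/7)(5/6)(3/5) = 0.333

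**5. Effect on the test.** If the censored subject leaves the denominator, 2/10 (p = 0.026) becomes 2/9 (p = 0.022), and 1/10 (p = 0.232) becomes 1/9 (p = 0.211). Neither decision changes.

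**The case against.** The strongest reply is that the route is narrow. Treatment normally runs to progression, and the last-dose floor then protects the event completely. The day-missing case also needs a short gap in the second half of one month. Partial dates can be queried in so small a trial, and the documents give no frequency for them. All of this stands and limits the size, but it does not remove the gap for subjects whose drug was stopped or held first.

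One could also point out that the running text of SAP 5.3.1 censors only subjects without documented progression. However, it refers to the table for the detail, and the table row covers therapy begun before a documented progression.

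Four stronger readings are tempting, and the documents do not support them:

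- **The error always favours the drug.** The 15th is a mid-month value and can err either way. With a true start on 3 May and progression on 10 May, the imputed 15 May keeps an event that the table would censor.
- **The median is raised as well.** In the cases with the largest shift in the 6-month rate it does not move: the curve is at 0.50 at week 12 (first illustration) and at 4.1 months (second) with or without the lost event. Losing an early event from a curve lying exactly at 50% could move it by one scan, but no general effect follows.
- **The trial's decision changes.** Step 5 shows no change when the subject is dropped. Counting the subject as progression-free would turn 1/10 into 2/10 (p from 0.232 to 0.026), but the SAP does not say so. How subjects censored before 6 months enter the exact test is a separate gap.
- **The stop/start rule is written backwards.** The rule is "If the imputed stop date is before start date, the stop date will be used as the start date", whereas SAP 8.2.2.2 has "If the imputed end date is before the start date, the start date will be used as the end date". The two are not alike. In 8.2.1.1 a partial stop is placed as late as possible (month-end or 31 December), so a stop before an imputed start shows that the start was put too late. A year-only start (1 July) with a stop in March (31 March) is an example: moving the start back agrees with the record, and the swap would keep an impossible start. In 8.2.2.2 a missing day becomes the first of the month, so there an imputed end can fall too early.

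**Conclusion.** The gap is real and limited. For a subject whose last dose precedes progression, and whose progression lies between the imputed and the true start of new therapy, the plan would censor a genuine IRC progression and raise the Kaplan-Meier 6-month rate. One such subject moves the illustrative rate from 20% to between 22% and 30%, or from 30% to at most 37.5%. The upper values arise only when the lost event is at the last scan before 6 months.

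The data sets, the date examples, the uniform start day and the frequency of 0 to 1 subject in 10 are assumptions; the documents supply none of them. The design, sample size and error rate are not in question. The rule should be settled before the primary analysis, so that nobody has to decide such a case with the result in view.

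**What to change.** Add to SAP 8.2.1.1: *If documented progression (IRC for the primary analysis, Investigator for the Investigator analysis) falls in the known month, or in the known year when only the year is recorded, the imputed start date will be no earlier than the day after progression, unless the record shows that therapy began before progression.* Where progression is on the last day of that month or year, the progression date itself will do, because the table censors only therapy begun before it.

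Leave the direction of the stop/start rule as it is. At most, limit it to imputed starts, so that an imputed stop never overwrites a fully recorded start. The subsection also announces a rule for completely missing start dates and gives none, which can be settled in the same edit.

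The cost is one or two SAP sentences and a line of programming. Sample size, level and power (0.837 with 9 evaluable) do not change. The downside is that a therapy truly begun shortly before progression in the same period would be counted as an event, which is the conservative direction.
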